7.3. Method of Treatment Assignment

Participants will be assigned to study treatment in accordance with the randomization schedule. The randomization code will be generated by GSK using a validated computerized system. Participants will be randomized using an interactive web response system (IWRS) RAMOS NG. The study will use central-based randomization to allocate treatments. Once a randomization number is assigned to a participant it cannot be reassigned to any other participant in the study.

Following the 2-week Run-in period and subject to satisfying all eligibility criteria, participants will be randomized 1:1 to one of the following double-blind treatments for the duration of the Treatment Period:

- GSK3772847 (10 mg/kg) administered intravenously
- Placebo administered intravenously

The duration of the Treatment Period for each participant is 16 weeks. Each Investigator will be provided with sufficient supplies to conduct the trial. Additional treatment kits will be supplied as needed to the sites. Details of how to use the IWRS system (RAMOS NG) to randomize participants and manage study treatment supplies (including dispensing) is provided in the RAMOS NG manual and SRM.

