10.2. Sample Size Determination

The study will randomize 74 participants per treatment arm with the aim of having 70 evaluable participants per arm. For the purpose of this study an evaluable participant is defined as a participant who completes the Week 16 clinic visit whilst remaining on IP or who withdraws from IP having met the primary endpoint. See Section 10.4.1 for how subjects who withdraw early from IP for reasons other than loss of asthma control are handled in the analysis.

In addition to testing the hypothesis in the overall population, the study will randomize a sufficient number of participants to evaluate trends in pre-defined subgroups (e.g. eosinophil strata).

The true proportion of participants that would experience a loss of asthma control on each treatment is unknown. However in a similar study of Dupilumab compared with placebo, the proportion of participants with loss of control were 6% and 44% for Dupilumab and placebo respectively. Table 4 gives the power to detect a statistically significant difference (at the two-sided 5% level) between the two treatments assuming the true proportion with loss of control on placebo is 44% and the true proportion with loss of control on active is 6%, 11%, 19% and 22% [Fleiss, 2003].

Table 4 Table of Power Achievable for Different Treatment Comparisons using N=70 per arm calculated using PASS

True proportion on Placebo	True proportion on GSK3772847	Reduction	Power
44%	6%	86%	> 99%
44%	11%	75%	> 99%
44%	19%	57%	90%
44%	22%	50%	80%

Assuming the true proportion with loss of control on placebo is 44%, then with 70 evaluable participants per arm, the study will have at least 80% power to detect a statistically significant difference between treatments assuming the true proportion with loss of control on GSK3772487 is at most 22% (Table 4).

With 70 evaluable participants per arm and assuming the true proportion with loss of control on placebo is 44%, the smallest observed difference that would lead to rejection of the null hypothesis (minimum detectable effect) is 31% corresponding to a proportion with loss of control on GSK3772847 of 28%.

There is a single primary endpoint so no adjustments are required for multiplicity.

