	 according to the pre-defined schedule (Section 5.1) Proportion of participants with ACQ-5 score increase from Baseline (measured at the end of Run-in) ≥0.5 point. Proportion of participants with a clinically significant asthma exacerbation or inability to titrate ICS according to the pre-defined schedule. In these analyses, the endpoint will be set to missing for participants who withdraw from IP prior to Week 16 for reasons other than loss of asthma control.
	Time to loss of asthma control will be analyzed using Kaplan-Meier analysis. Percentiles for time to loss of control will be presented for both treatment groups, along with graphical survival plots. Any early withdrawals from IP that did not experience loss of control will be censored. Results will be presented for both of the two eosinophil strata separately, and combined.
	The following endpoints will be analyzed using repeated logistic regression. This analysis will be repeated including an additional term for eosinophil strata by treatment by visit interaction to provide estimates for the two eosinophil strata separately:
	 Proportion of ACQ-5 responders (a ≥0.5 point improvement from baseline at Week 16) Proportion of SGRQ responders (at least a 4 unit improvement from
	baseline at Week 16 These analyzes will be performed using two different methods for handling missing data:
	If endpoint at a visit is missing then the responder status is set to missing
	2) If endpoint at a visit is missing and the endpoint is also missing at all subsequent visits then the responder status is set to non-responder. The odds ratio, 95% CI and p-value for the comparison of GSK3772847 with placebo will be presented for all models.
	Mixed model repeated measures will be used to analyze the following endpoints. The baseline value of each endpoint will be included along with baseline*visit and treatment*visit interactions. Treatment differences, 95% confidence intervals and p-values will be presented.
	 Change from baseline in ACQ-5 absolute score Change from baseline in SGRQ total score Change from baseline in Pre-bronchodilator FEV1
	Change from baseline in FeNO This analysis will be repeated including an additional term for eosinophil

Endpoint	Statistical Analysis Methods
	strata by treatment by visit interaction to provide estimates for each eosinophil strata separately. No adjustment will be made for missing data.

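### Time to loss of asthma control is described by Kaplan-Meier percentiles and plots with no between-arm time-to-event estimate, and at the protocol's planning rates a median is not expected in either arm

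*Protocol*

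**What the plan says.** Section 4 lists time to loss of asthma control among the secondary endpoints under an objective framed as a comparison with placebo. Section 10.4.1 gives the method as Kaplan-Meier analysis and describes the output: "Percentiles for time to loss of control will be presented for both treatment groups, along with graphical survival plots". Participants who stop investigational product (IP) without the event are censored, and results are shown for each eosinophil stratum and combined. The percentile levels are not named.

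The same table gives effect measures for the other secondary efficacy endpoints whose method it sets out. The component proportions follow the primary analysis (ratio with credible interval, and odds ratio with confidence interval and p-value). The responder endpoints get odds ratios, and the mixed-model endpoints get treatment differences with intervals and p-values. A separate list defers some methods to the reporting and analysis plan: hospitalisation or ER visits, PEF, symptom score, rescue use and awakenings. Time to loss of control is not on that list.

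The planning rates are in Section 10.2: "Assuming the true proportion with loss of control on placebo is 44%, then with 70 evaluable participants per arm", the protocol states that "the study will have at least 80% power to detect a statistically significant difference between treatments" if the active rate is no higher than 22%. Table 4 also covers active rates of 19%, 11% and 6%.

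**The concern.** A Kaplan-Meier percentile exists only if the curve falls far enough within follow-up. Under the protocol's assumptions fewer than half of either arm loses control by Week 16, so the usual summary, the median, is not expected in either arm. The difficulty grows as the drug works better, because fewer active participants have the event.

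Without a between-arm measure, the report could show two curves and a table largely marked as not reached, leaving readers to judge any delay in loss of control by eye. This is also the one stated analysis of the loss-of-control event that uses the follow-up of participants who stop IP for other reasons up to the time they stop. The primary analysis sets them to missing, and its sensitivity analysis counts them as failures.

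**Working it through.** **Inputs.** From Section 10.2: "The study will randomize 74 participants per treatment arm with the aim of having 70 evaluable participants per arm", a placebo rate of 44%, and active rates of 22%, 19%, 11% and 6%. The test level is that of Table 4: "Table 4 gives the power to detect a statistically significant difference (at the two-sided 5% level) between the two treatments". Allocation is 1:1 (Section 7.3) and the endpoint runs over Weeks 0 to 16 (Section 4).

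**Reproducing Table 4.** Two-proportion test, pooled variance, no continuity correction, 44% versus 22%:

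- Null SE = √(2 × 0.33 × 0.67 / 70) = 0.0795, and 1.96 × 0.0795 = 0.156.
- Alternative SE = √((0.44 × 0.56 + 0.22 × 0.78) / 70) = 0.0773.
- Power = Φ((0.22 − 0.156) / 0.0773) = 79.7%, against 80% stated.

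The other rows give 89.8% (19%), 99.5% (11%) and 99.98% (6%), against 90%, over 99% and over 99%. A continuity correction gives 74.1% in the 22% row and does not match. The inputs are therefore read correctly.

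**Chance that a percentile is estimable.** With complete 16-week follow-up, the q-th percentile exists only if at least ⌈q × 70⌉ participants in the arm have the event, so the chance is P(Binomial(70, p) ≥ ⌈0.01q × 70⌉) for q in percent. Expected events are 70 × 0.44 = 30.8 on placebo and 70 × 0.22 = 15.4 on active.

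| Percentile (events needed) | Placebo 44% | Active 22% | Active 19% | Active 11% | Active 6% |
|---|---|---|---|---|---|
| 10th (7) | ~100% | 99.7% | 98.7% | 66.2% | 12.6% |
| 20th (14) | ~100% | 70.1% | 46.3% | 1.9% | 0.01% |
| 25th (18) | 99.95% | 26.7% | 10.3% | 0.04% | ~0 |
| 50th (35) | 18.6% | ~0 | ~0 | ~0 | ~0 |

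The 75th percentile is out of reach in every column. At 44% versus 22%, of the six cells formed by quartile and arm, only the placebo 25th percentile is expected to be filled. With 74 per arm the placebo median is reached in 17.8% of trials and the active 25th percentile in about 26%.

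**By stratum.** A stratum at the 30% target has about 0.30 × 70 = 21 per arm. With the same rates, the placebo 25th percentile is reached in 95% and the placebo median in 29%. On active at 22% the figures are 31% and 0.2%.

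**What a between-arm summary would give at 44% versus 22%.**

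- Difference in Week 16 proportions, full follow-up: 0.22 ± 1.96 × 0.0773, or about 0.07 to 0.37. No proportional-hazards assumption is needed.
- Hazard ratio under proportional hazards: ln(0.78) / ln(0.56) = 0.43. The SE of its logarithm is √(1/30.8 + 1/15.4) = 0.31, giving a 95% CI of about 0.23 to 0.79 on about 46 events.
- Log-rank power: Φ(√(46.2/4) × |ln 0.43| − 1.96) ≈ 82%. A simulation with constant hazards and event times moved to the next scheduled visit gave 80%.

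**The case against.** The strongest reply has four parts.

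**The curves already compare the arms.** Survival plots are specified beside the percentiles, and they show the event-free proportion throughout the 16 weeks. A reader might infer that percentiles are the only output and that no comparison is possible. The text does not support that. What is missing is a stated estimate, interval or test.

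**The levels and rates are not fixed facts.** The protocol names no percentiles, so it does not follow that whatever is reported will be inestimable: at 44% versus 22% the 10th is nearly certain in both arms and the 20th likely. Section 10.2 also calls the true rates unknown. If placebo loss of control were 50% or 60% (assumed values, outside the protocol), the placebo median would be reached in 55% or 97% of trials. This limits the claim to the planning rates. It does not rescue the median there, or the 10th percentile at 6% active.

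**The event is already compared.** A reader might infer that no treatment effect on loss of control is estimated. Section 10.4.1 estimates one in the primary analysis, and log-rank power is close to the binary test's 80%. This stands and keeps the point small.

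**Detail belongs in the analysis plan.** Handling of ties and model specification do. However, the protocol states a method for this endpoint, leaves it off the deferred list, and gives effect measures to its neighbours. A descriptive analysis is defensible in a Phase IIa study judged on posterior probabilities, but it fits poorly with an objective framed against placebo.

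**Conclusion.** The point holds as a minor one. The stated method for a comparative secondary endpoint yields no between-arm time-to-event measure, and the most familiar percentiles are mostly not expected at the protocol's own rates. No sample-size figure, primary result or success criterion is affected.

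The percentile chances assume complete 16-week follow-up and, for the stratum figures, equal rates across strata. The hazard-ratio figures assume proportional hazards, which the protocol does not state and which the stepwise background withdrawal between Visits 4 and 8 does not guarantee. The 0.43 therefore shows feasibility and is not a planned effect.

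A reader might also infer that this is the only analysis using partial follow-up from participants who stop IP. That holds only for the loss-of-control event. The repeated-measures analyses use such data for other endpoints, and the planned loss is small (4 of 74 per arm, 5.4%).

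**What to change.** In Section 10.4.1, keep the Kaplan-Meier curves and any percentiles that can be estimated. Add, as the main summary, Kaplan-Meier cumulative proportions with loss of control at Week 16 by arm, each with a 95% confidence interval, and their difference with a 95% confidence interval. These need no proportional-hazards assumption and use the follow-up of censored participants, provided censoring is unrelated to the risk of the event.

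Support this with a log-rank test and a Cox hazard ratio with 95% confidence interval, both stratified by the randomisation eosinophil stratum, and check proportional hazards. Handling of ties at scheduled visits can be set in the reporting and analysis plan.

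The cost is a change of wording and some programming. No further data, visits or participants are required.

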10.4.2. Safety Analyses

All safety analyses will be performed on the mITT Population.

Endpoint	Statistical Analysis Methods
Primary	There is no primary safety analysis.
Secondary	The following secondary safety endpoints will be analyzed descriptively by treatment group:
	 Incidence and frequency of AEs and SAEs Vital signs 12-lead ECG 24 hours Holter Clinical laboratory evaluation Incidence of and titres of anti-GSK3772847 antibodies. Details will be described in the reporting and analysis plan

Adverse events (AEs) will be coded using the standard GSK dictionary, Medical Dictionary for Regulatory Activities (MedDRA), and grouped by body system. The number and percentage of subjects experiencing at least one AE of any type, AEs within each body system and AEs within each preferred term will be presented for each treatment group. Separate summaries will be provided for all AEs, drug related AEs, fatal

AEs, non-fatal SAEs, adverse events of special interest (AESIs) and AEs leading to withdrawal.

207597

Deaths and SAEs, if applicable, will be documented in case narrative format.

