At Visit 4 (i.e. two weeks after Randomization) the open label background therapy will be switched from FP/Salmeterol 500/50 mcg BID to FP 500 mcg BID for 2 weeks. This will mark the beginning of the FP titration period. Every two weeks for the next six weeks the dose of FP will be reduced by approximately 50 % (i.e. FP 250 mcg BID at Visit 5 for 2 weeks, FP 100 mcg BID at Visit 6 for 2 weeks, then FP 50 mcg BID at Visit 7 for 2 weeks) until complete FP discontinuation at Visit 8, provided that the participant does not meet any of the loss of asthma control criteria. If any of the pre-defined criteria for loss of asthma control are met during the Treatment Period, participants will be withdrawn from the investigational product (IP) and should resume regular treatment for their asthma, as determined by the investigator.

Participants will be monitored for loss of asthma control through daily use of an eDiary and twice-daily PEF measurements. The participants will use the eDiary to record asthma symptoms, rescue medication use, and nocturnal awakenings due to asthma symptoms requiring rescue medication use. This information will be transmitted daily to a centralized server and available to the investigators. Alerts for pre-defined changes in PEF or asthma symptoms, indicative of worsening asthma, will be programmed into the eDiary with prompts to the participants to contact the investigator if any of the alert criteria are met (Section 9.1.2.3). Additionally, email notifications will be sent to the investigator, if any of the alert criteria are met, as soon as the data is transmitted to the centralized server. The investigator will make every effort to contact the participants in order to discuss the participants' symptoms and evaluate whether they experienced loss of asthma control.

For participants who receive all four doses of blinded study treatment, an End of Treatment Period (ETP) Visit will be performed 4 weeks after the final dose of the blinded study treatment is administered at Week 12. Participants should resume regular treatment for their asthma, as determined by the investigator, after protocol defined study assessments are completed. Three Follow-up visits will be performed 4, 8, and 12 weeks (Week 20, Week 24, and Week 28) after the ETP Visit for safety assessments.

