For participants who discontinue IP early, but have not withdrawn consent to participate in the study, an early withdrawal (EW) visit will be performed 4 weeks after the last dose of blinded study treatment. These participants should continue in the study and complete all assessments at the remaining protocol-defined visits until their EW visit. Participants should resume regular treatment for their asthma, as determined by the investigator. Three Follow-up visits will then be performed 4, 8, and 12 weeks after the EW visit for safety assessments.

Participants who discontinue IP early and withdraw consent to participate in the study should complete as many assessments planned for the EW visit as possible.

Following randomization participants will return to the clinic at least every 2 weeks for scheduled FP dose titration and assessment of asthma control until the last dose of blinded study treatment (Visit 9).

Albuterol/salbutamol will be provided for symptomatic relief to be used on an as needed basis from Screening through to the ETP visit.

The maximum total duration of the study is approximately 33 weeks.

An independent Safety Review Committee (iSRC) will periodically review unblinded safety data to protect and maintain participant safety whilst maintaining scientific validity. Members of the iSRC will be independent of the project. The data will include, but not necessarily be limited to SAEs, Holters, and ECGs. Details are described in the iSRC Charter.

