8. DISCONTINUATION CRITERIA

8.1. Discontinuation of Study Treatment

Participants that permanently stop study treatment are encouraged to remain in the study. Participants have the right to discontinue study treatment before the end of the study. A participant may also be asked to discontinue study treatment at the Investigator's discretion.

Participants who withdraw from study treatment prematurely (for any reason) should, where possible, continue to be followed-up until the completion of the Safety Follow-up assessments:

• For participants who discontinue IP early, but have not withdrawn consent to participate in the study, an early withdrawal (EW) visit will be performed 4 weeks after the last dose of blinded study treatment. These participants should continue in the study and complete all assessments at the remaining protocol-defined visits until their EW visit. Participants should resume regular treatment for their asthma, as determined by the investigator. Three Follow-up visits will then be performed 4, 8, and 12 weeks after the EW visit for safety assessments.

CONFIDENTIAL

• Participants who discontinue IP early and withdraw consent to participate in the study should complete as many assessments planned for the EW visit as possible.

If this is not possible, the Investigator must encourage the participant to participate in as much of the study as they are willing (or able) to.

A participant may be withdrawn from study treatment at any time. A reason for premature discontinuation of study treatment (e.g., AE, lack of efficacy [including loss of asthma control], protocol deviation, Investigator discretion, consent withdrawn etc.) must be captured in the eCRF.

A participant must be withdrawn from study treatment if any of the following stopping criteria are met:

- 1. Liver Chemistry: Meets any of the protocol-defined liver chemistry stopping criteria.
- 2. QTc: Meets any of the protocol-defined stopping criteria.
- 3. Pregnancy: Positive pregnancy test.
- 4. Participant meets at least one of the following criteria for 'loss of asthma control':
 - ACQ-5 score increase from baseline (measured at Visit 2) \geq 0.5 point.
 - Pre-bronchodilator FEV1 decrease from baseline (measured at Visit 2) >7.5 %.
 - Inability to continue inhaled corticosteroid titration which is assessed and determined by the investigator at any time point following randomization, including on scheduled clinic visits.

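### Section 10.4.2 states only crude AE percentages by arm, but loss of control shortens AE observation, so an effective drug would be observed somewhat longer; add person-time rates beside the percentages

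*Protocol*

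**What the plan says.** **Summary measure.** Section 10.4.2 of the protocol says "The following secondary safety endpoints will be analyzed descriptively by treatment group". The list below that sentence starts with the incidence and frequency of AEs and SAEs. The summary it then describes is "The number and percentage of subjects experiencing at least one AE of any type", with the same by body system and preferred term for each arm. No person-time or exposure-adjusted measure is named. The same section adds: "Details will be described in the reporting and analysis plan".

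**Stopping treatment.** Section 8.1 says "A participant must be withdrawn from study treatment if any of the following stopping criteria are met", and loss of asthma control is one of the criteria. Section 5.1 agrees: "participants will be withdrawn from the investigational product (IP) and should resume regular treatment for their asthma".

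**Follow-up after stopping.** In Section 5.1, "an early withdrawal (EW) visit will be performed 4 weeks after the last dose of blinded study treatment", and then "Three Follow-up visits will then be performed 4, 8, and 12 weeks after the EW visit for safety assessments". For those who receive all four doses: "Three Follow-up visits will be performed 4, 8, and 12 weeks (Week 20, Week 24, and Week 28) after the ETP Visit for safety assessments". Section 9.2.1 collects AEs until the follow-up visit.

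The synopsis places Weeks 20, 24 and 28 beside the combined ETP/EW visit, which could suggest a fixed calendar. Sections 5.1 and 8.1 and the note to the Schedule of Activities tie follow-up to the actual EW visit, and I have used that reading.

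**The concern.** The event that shortens AE observation is the primary endpoint, so the length of observation depends on treatment whenever treatment works. The intensity of observation depends on it too. During treatment, visits are at least every two weeks, with frequent laboratory tests and with ECGs on dosing days. In follow-up, visits are every four weeks, with no ECG or Holter and laboratory tests only at the last one.

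A percentage of subjects with at least one event rises with time under observation. If the two arms had the same AE rate, the better-controlled arm would still tend to show the higher percentage. Section 9.2 keeps asthma exacerbations and worsening out of the AE record unless they are serious, so extra asthma events on placebo would largely not restore the balance.

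The secondary safety objective is a comparison with placebo, and the risk assessment discusses cardiac findings and infections. A reader of the tables needs to be able to tell longer observation from a signal.

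**Working it through.** **Inputs from the protocol.** Doses at Weeks 0, 4, 8 and 12 (Section 5.1). EW or ETP visit at last dose + 4 weeks, and last follow-up 12 weeks later (Section 5.1). Loss of control 44% on placebo and 6%, 11%, 19% or 22% on active, with 70 evaluable per arm (Section 10.2).

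**Inputs assumed, because the protocol gives no figure.** The timing of loss of control; a constant AE hazard, equal in both arms; and the underlying AE incidence over 28 weeks (50%, with 20% and 70% as a range).

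**Step 1: reproduce the plan's own figure.** The check is power for 44% vs 22%, n = 70 per arm, two-sided 5%, pooled variance under the null, no continuity correction.
- Null SE = √(2 × 0.33 × 0.67 / 70) = 0.0795, so the critical difference is 1.96 × 0.0795 = 0.156.
- Alternative SE = √((0.44 × 0.56 + 0.22 × 0.78) / 70) = 0.0773.
- Power = Φ((0.22 − 0.156) / 0.0773) = 79.7%, against a stated 80%.

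The other rows of Table 4 give 89.8% (stated 90%), 99.5% and 99.98% (both stated as above 99%). The loss-of-control rates are therefore being read as the protocol intends.

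**Step 2: end of AE observation = last dose + 4 + 12 weeks.**
- 1 dose: Week 16
- 2 doses: Week 20
- 3 doses: Week 24
- 4 doses: Week 28

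A participant who loses control after dose 4 is observed as long as one who never loses it.

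**Step 3: mean observation time = 28(1 − p) + p × E**, where p is the proportion losing control and E is the mean end week among them.

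| Assumed timing of loss | E | Placebo 44% | Active 22% (ratio) | Active 6% (ratio) |
|---|---|---|---|---|
| (a) evenly over the three intervals from Week 4 | 24 | 26.24 | 27.12 (1.03) | 27.76 (1.06) |
| (b) evenly over all four intervals | 22 | 25.36 | 26.68 (1.05) | 27.64 (1.09) |
| (c) all before dose 2 (extreme) | 16 | 22.72 | 25.36 (1.12) | 27.28 (1.20) |

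Example, (b) placebo: 28 × 0.56 + 0.44 × 22 = 15.68 + 9.68 = 25.36 weeks.

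**Step 4: crude AE incidence with no true AE difference.** For 50% incidence over 28 weeks the hazard is h = ln 2 / 28 = 0.0248 per week. Incidence to week t is 1 − exp(−ht): 32.7% at Week 16, 39.0% at Week 20, 44.8% at Week 24 and 50% at Week 28. Arm incidence = 0.50(1 − p) + p × (mean incidence among those losing control).

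| Timing | Placebo 44% | Active 22% | Excess, points | Active 6% | Excess, points |
|---|---|---|---|---|---|
| (a) | 47.6% | 48.8% | 1.2 | 49.7% | 2.0 |
| (b) | 46.3% | 48.2% | 1.8 | 49.5% | 3.2 |
| (c) | 42.4% | 46.2% | 3.8 | 49.0% | 6.6 |

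Over underlying incidences of 20% to 70%, the full range of the excess is 0.6 points (timing a, 22%, incidence 20%) to 7.7 points (timing c, 6%, incidence 70%). Under the same assumptions a rate per person-time has a ratio of 1.0.

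**Step 5: doses received.** Under timing (b) the mean number of doses is 3.34 on placebo, against 3.67 (22%) or 3.91 (6%) on active. Longer observation and greater exposure therefore come together.

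**The case against.** The strongest reply is that the protocol closes nothing off. Section 10.4.2 is descriptive, has no primary safety analysis, does not say that percentages will be the sole measure, and leaves details to the reporting and analysis plan, where exposure-adjusted rates are often placed. This stands. A reader might infer that the protocol commits to percentages alone; the text supports only that they are the one AE measure it states.

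A reader might also infer that an effective drug would show more AEs purely by being watched longer. That does not follow. Participants who keep control receive more doses, so part of an excess could be a true exposure effect. Equal hazards are also an assumption. Those who lose control resume regular asthma treatment, some with oral corticosteroid, and Section 3.3.2 itself links a lower inhaled steroid dose to fewer steroid-related events, which could work in the other direction.

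A larger effect, of 3 to 9 points, can be obtained by counting AEs only to last dose + 4 weeks at a hazard of 0.04 per week, with half of all losses before dose 2 at the top of that range. The protocol does not set that window for AE summaries, and nothing in it supports that timing: salmeterol is removed at Week 2, but the first reduction in fluticasone dose is at Week 4 and it stops only at Week 10.

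Finally, the effect is small against sampling error. With 74 per arm and incidence near 50%, the 95% half-width for a difference is about 1.96 × √(2 × 0.25 / 74) = 16 points. Unblinded review of SAEs, Holters and ECGs by the safety review committee also covers the cardiac risk. Both points lower the priority. They do not remove the imbalance, which is systematic whenever the drug works.

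**Conclusion.** The point holds in a limited form and is a cheap improvement. The one AE measure Section 10.4.2 states does not account for an observation time that the primary endpoint itself shortens. At the protocol's planning rates the active arm would be observed about 3-12% longer (44% vs 22%) or 6-20% longer (44% vs 6%). With no true AE difference, that adds about 1-4 or 2-7 points to its crude AE percentage.

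These figures rest on equal constant hazards, 50% underlying incidence and an assumed timing of loss of control. The upper ends require all losses before dose 2. An excess seen in the trial could not be put down to observation time alone, because the number of doses differs too.

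**What to change.** In Section 10.4.2, state that person-time and exposure-adjusted rates of AEs, SAEs and AESIs will be presented by arm beside the numbers and percentages, for two periods: on treatment (first dose to last dose + 4 weeks) and the whole observation period. State that the percentages will be read alongside these rates.

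The cost is a few extra tables from dates already collected. The rates assume a roughly constant hazard. If events cluster early, for example around infusions, dividing by longer time in the active arm would dilute a real difference. The rates should therefore supplement the percentages and not replace them.
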